Losmapimod tablets 15 mg (provided as two 7.5 mg tablets) PO BID or matching placebo tablets PO BID for 48 weeks (or 24 weeks if rolled over to the OLE under protocol version 3.0, prior to the COVID-19 pandemic)

Open-Label Extension:

Losmapimod tablets 15 mg (provided as two 7.5 mg tablets) PO BID until study drug approval or until the study is discontinued by the sponsor

Study drug should be administered with food.

Sample Size:

Assuming an effect size of 0.70, a sample size of 68 subjects (34 subjects per group) will be needed to provide 80% power with a 2-sided test at a 0.05 significance level to detect a difference between losmapimod and placebo in change from baseline in DUX4 activity in affected skeletal muscle after 16 or 36 weeks (depending upon when the muscle biopsy was performed) during the placebo-controlled treatment period. Assuming that approximately 10% of subjects will be non-evaluable, approximately 76 subjects will be randomly assigned at a 1:1 ratio to losmapimod and placebo (38 subjects per group).

Statistical Methods:

Continuous variables will be summarized using the mean, standard deviation, median, minimum, and maximum. Categorical variables will be summarized using frequency counts and percentages. All statistical tests will be 2-sided and performed using a 0.05 significance level.

Fulcrum Therapeutics

Losmapimod

Protocol FIS-002-2019, Version 4.0 (COVID-19 Pandemic Emergency Amendment)

10 April 2020

The primary endpoint for the placebo-controlled treatment period will be evaluated using an analysis of covariance (ANCOVA) model to analyze the change from baseline in DUX4 activity in affected skeletal muscle after 16 weeks or 36 weeks of treatment, with repeat number category and treatment group as fixed effects and baseline DUX4 activity in affected skeletal muscle as a covariate. Least-square (LS) mean, standard error, and 95% confidence interval (CI) of the LS mean will be provided for each treatment group. The difference in LS means between treatment groups and 95% CI of the difference will also be calculated. The final p-value will be compared against the significance level of approximately 0.05. All available data will be used. The full analysis set will be used for the primary analysis in the placebo-controlled treatment period.

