7.6.8 Interim Analyses

One IA will be performed when a minimum of 22 paired muscle biopsies are completed. A group sequential method (O'Brien-Fleming Spending Function) will be used to ensure an

Fulcrum Therapeutics Losmapimod
 Protocol FIS-002-2019, Version 4.0 (COVID-19 Pandemic Emergency Amendment) 10 April 2020
 overall significance level of 0.05 (double-sided) due to multiple looks at the DUX4 primary endpoint, if the IA is deemed necessary by the Sponsor.

- With a sample size of approximately 22 subjects at IA, the test alpha at IA is approximately 0.001, and the final test alpha is 0.05. If the p-value from the test is <0.001 , then the study may be stopped for efficacy, or continue as planned as decided by the Sponsor. Cumulative exit probability under the alternative hypothesis is approximately 2.3% and approximately 82.3% at the IA and final analysis, respectively (SAS Version 9.4; nQuery 8 – Power and Sample Size for Group Sequential Trials, Version 8.5.1.0).
- With a sample size of 32 subjects at IA, the test alpha at IA is approximately 0.004, and the final test alpha is 0.048. If the p-value from the test is <0.004 , then the trial may be stopped for efficacy, or continue as planned as decided by Sponsor. Cumulative exit probability under the alternative hypothesis is approximately 13.9% and approximately 82.2% at the IA and final analysis, respectively (SAS Version 9.4; nQuery 8 – Power and Sample Size for Group Sequential Trials, Version 8.5.1.0).

The alphas at the time of the IA for sample sizes ranging from 22 to 32 are provided in [Table 7-1](#):

Table 7-1 Alpha at Interim Analysis and Final Analysis for Different Sample Sizes at Interim Analysis (O'Brien-Fleming Method)

Interim Analysis Sample Size	Alpha at Interim Analysis	Alpha at Final
22	0.000567	0.049755
23	0.000736	0.049685
24	0.000951	0.049596
25	0.001203	0.049493
26	0.001474	0.049384
27	0.001803	0.049253
28	0.002173	0.049107
29	0.002556	0.048959
30	0.003005	0.048787
31	0.003496	0.048602
32	0.004027	0.048405

Fulcrum Therapeutics

Protocol FIS-002-2019, Version 4.0 (COVID-19 Pandemic Emergency Amendment)

Losmapimod

10 April 2020

8 Data Quality Assurance

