4.1. Reporting Conventions

All data summaries, unless otherwise noted, will be presented by treatment group:

- Losmapimod 15 mg BID
- Placebo BID

The following conventions will be used for all the data presentations and analyses unless otherwise specified.

Appropriate descriptive statistics will be computed and displayed for both continuous and categorical variables. For continuous and quantitative variables, summaries will include n (number of subjects with non-missing data), mean, standard deviation (SD), Q1 (first quartile), Q3 (third quartile), median, minimum and maximum. Reporting conventions for descriptive statistics will follow the [REDACTED] Standard TLF Guidelines. For categorical variables, summaries will include the number and percentage of subjects who are in a particular category. Percentages will be computed based on the number of non-missing data points for patients in the applicable analysis set. Reporting of percentages will follow the [REDACTED] standard TLF Guidelines.

A total column will be presented for all demographic, baseline characteristic, baseline disease characteristic, protocol deviation, and prior and concomitant medication summaries.

All data will be listed by treatment group, FSHD repeat number category, subject ID, Ricci score, sex and visit date, if available. Any repeat assessments or additional assessments, along with any unscheduled visits, will be presented in the listings. Sort order of data listings will be treatment group, FSHD repeat number category, subject ID, and visit date, if available.

Statistical tests will be 2-sided and will be conducted at the significance level provided in [Table 12-1](#)), unless otherwise specified. P-values will be reported to 4 decimal places, with p-values less than 0.0001 reported as “<0.0001”.

All analyses will be performed using Statistical Analysis Software (SAS®, release 9.4 or higher). A separate document as an appendix to this SAP will contain the tables, listings, and figure (shells).

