The quantification of gene expression and normalization of qPCR are conducted at a central laboratory (Q2 Lab Solutions) in a blinded fashion, with no access to treatment assignment information. A total of six DUX4-regulated gene transcripts (CCNA1; KHDC1L; MBD3L2; PRAMEF6; SLC34A2; ZSCAN4) have been pre-selected for inclusion in the mean DUX4 score. DUX4 Score 1 will be used for the primary analysis. A second and third composite scores (DUX4 Score 2 and DUX4 Score 3, respectively) will be used for sensitivity analysis. For details on assay validation, gene subset selection criteria/process, and derivation of DUX4 Score, see [Appendices 15.1 – 15.5](#).

DUX4 score 1 will be summarized as change from baseline to either Week 16 or Week 36. Study subjects can only have one post-baseline biopsy (either Week 16 or Week 36, but not both). If the pre-treatment or on-treatment DUX-4 results are unavailable, then the assessment is considered missing. See [Section 8.2.1](#) for details of missing data handling for DUX4 Score.

For each treatment, descriptive statistics of aberrant DUX4 activity will be presented at Baseline and post-baseline (Week 16 or Week 36) as well as change from baseline. An ANCOVA model

will be used to analyze the change from baseline in DUX4 activity in affected skeletal muscle, which is the response variable, with repeat number category and treatment group as fixed effects and baseline DUX4 activity in affected skeletal muscle as a covariate. Within-group least-squares (LS) means, the associated standard errors (SEs) and 2-sided 95% CIs, treatment differences in LS means and the associated 2-sided 95% CIs and 2-sided p-values will be derived from the model and presented in the table. If the model-based p-value of the treatment difference in the change from baseline is less than the final alpha provided in [Table 12-1](#), the difference between two treatment groups will be determined to be statistically significant.

Similar methods will be used to analyze the change from baseline in DUX4 activity within subgroups identified in [Section 4.6](#) to evaluate consistency of treatment effects across the subgroups. For the repeat category subgroup analysis, the repeat category will be excluded as fixed effect from the model.

The LS mean change from baseline by visit of the DUX4 activity will be graphically presented.

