Initially, no interim analysis for efficacy was planned. However, based on protocol version 4.0 (COVID-19 Pandemic Emergency Amendment) dated 10Apr2020, an interim analysis was included to provide timely data to inform the further development of losmapimod for the treatment of FSHD.

One IA will be performed when a minimum of 22 paired muscle biopsies are completed. A group sequential method (O'Brien-Fleming Spending Function) will be used to ensure an overall significance level of 0.05 (double-sided) due to multiple looks at the DUX4 primary endpoint, if the IA is deemed necessary by the Sponsor.

- With a sample size of approximately 22 subjects at IA, the test alpha at IA is approximately 0.001, and the final test alpha is 0.05. If the p-value from the test is <0.001 , then the study may be stopped for efficacy, or continue as planned as decided by the Sponsor. Cumulative exit probability under the alternative hypothesis is approximately 2.3% and approximately 82.3% at the IA and final analysis, respectively (SAS Version 9.4; nQuery 8 – Power and Sample Size for Group Sequential Trials, Version 8.5.1.0).
- With a sample size of 32 subjects at IA, the test alpha at IA is approximately 0.004, and the final test alpha is 0.048. If the p-value from the test is <0.004 , then the trial may be stopped for efficacy, or continue as planned as decided by Sponsor. Cumulative exit probability under the alternative hypothesis is approximately 13.9% and approximately 82.2% at the IA and final analysis, respectively (SAS Version 9.4; nQuery 8 – Power and Sample Size for Group Sequential Trials, Version 8.5.1.0).

The alpha at the time of the IA for sample size ranging from 22 to 32 are provided in [Table 12-1](#)

Table 12-1 Alpha at Interim Analysis and Final Analysis for Different Sample Sizes at Interim Analysis (O'Brien Fleming Method)

Interim Analysis Sample Size	Alpha at Interim Analysis	Alpha at Final
22	0.000567	0.049755
23	0.000736	0.049685
24	0.000951	0.049596
25	0.001203	0.049493
26	0.001474	0.049384
27	0.001803	0.049253
28	0.002173	0.049107
29	0.002556	0.048959
30	0.003005	0.048787
31	0.003496	0.048602
32	0.004027	0.048405

The DUX4, PK, demographics, disposition data and sub-group analysis on the DUX4 endpoint ([Section 4.6, #1 to #5](#) and [#11](#)) will be presented to the Sponsor as group-level summaries of the unblinded data with associated p-values. The respective tables are indicated in the List of Planned Summary Tables.

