15.8. List of Planned Summary Tables

TLF	Table Number	Title	Analysis Set	Unique (U)/ Repeat (R)	Section	Efficacy/ Safety/ Standard	Topline	IA
Table	14.1.1	Subject Disposition	FAS	U	5.1	Standard		Y
Table	14.1.2	Protocol Deviations	FAS	U	5.2	Standard		
Table	14.1.3.1	Demographics	FAS	U	6.1	Standard	Y	Y
Table	14.1.3.2	Demographics	Safety Analysis Set	R	6.1	Standard		
Table	14.1.4.1	Baseline Disease Characteristics	FAS	U	6.2	Standard	Y	
Table	14.1.4.2	Baseline Disease Characteristics	Safety Analysis Set	R	6.2	Standard		
Table	14.1.5	Medical History	FAS	U	6.3	Standard		
Table	14.1.6.1	Prior Medications	Safety Analysis Set	U	7.1.1	Standard		
Table	14.1.6.2	Concomitant Medications	Safety Analysis Set	R	7.1.2	Standard		
Table	14.1.7.1	Study Drug Exposure	Safety Analysis Set	U	7.2.1	Standard		
Table	14.1.7.2	Drug Compliance	Safety Analysis Set	U	7.2.2	Standard		
Table	14.2.1.1	Summary of Losmapimod Concentrations by Scheduled Time and Specimen Type	PK Analysis Set	U	10	Efficacy		Y
Table	14.2.1.1.1	Summary of Losmapimod Concentrations by Scheduled Time and Specimen Type	Open-label losmapimod (Pre-COVID-19) Analysis Set	R	10	Efficacy		
Table	14.2.1.2.1	Summary of Target Engagement Estimates in Blood	PD analysis set	U	11	Efficacy	Y	
Table	14.2.1.2.2	Summary of Target Engagement Estimates in Blood by Baseline Repeat Category	PD analysis set	U	11	Efficacy		
Table	14.2.1.2.3	Summary of Target Engagement Estimates in Blood by Baseline Clinical Severity Score	PD analysis set	R	11	Efficacy		
Table	14.2.1.2.4	Summary of Target Engagement Estimates in Blood by Sex	PD analysis set	R	11	Efficacy		
Table	14.2.1.2.3.1	Summary of Target Engagement Estimates	Open-label losmapimod (Pre-COVID-19) Analysis Set	R	10	Efficacy		
Table	14.2.2.1.1	Change from Baseline in DUX4 Activity (DUX4 Score 1)	FAS	U	8.1	Efficacy	Y	Y

TLF	Table Number	Title	Analysis Set	Unique (U)/Repeat (R)	Section	Efficacy/Safety/Standard	Topline	IA
Table	14.2.2.1.2	Change from Baseline in DUX4 Activity (DUX4 Score 1) by Baseline Repeat Category	FAS	U	8.1	Efficacy	Y	Y
Table	14.2.2.1.3	Change from Baseline in DUX4 Activity (DUX4 Score 1) by Baseline DUX4 Score 1	FAS	R	8.1	Efficacy	Y	Y
Table	14.2.2.1.4	Change from Baseline in DUX4 Activity (DUX4 Score 1) by Sex	FAS	R	8.1	Efficacy	Y	Y
Table	14.2.2.1.5	Change from Baseline in DUX4 Activity (DUX4 Score 1) by Fat Fraction at Biopsy Site	FAS	R	8.1	Efficacy	Y	Y

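### No interval matched to the stopping boundary is planned for the interim DUX4 look: an ordinary 95% CI there, or after an early stop, does not correspond to the interim test level

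*Protocol*

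**What the plan says.** **Interval.** For the primary endpoint, the Protocol (Synopsis and 7.6.2) states: "The difference in LS means between treatment groups and 95% CI of the difference will also be calculated". SAP 8.2 does the same for the ANCOVA: "treatment differences in LS means and the associated 2-sided 95% CIs and 2-sided p-values will be derived from the model and presented in the table". SAP addendum 5.2 revisits Table 14.2.2.1.1 and adds a log-scale ANCOVA, again with 95% intervals.

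**Test level.** Protocol 7.6.8 and SAP 12 use O'Brien-Fleming spending to hold an "overall significance level of 0.05 (double-sided) due to multiple looks at the DUX4 primary endpoint". Table 7-1 (Table 12-1 in the SAP) gives an interim alpha of 0.000567 at 22 pairs, rising to 0.004027 at 32. The matching final alphas are 0.049755 and 0.048405. SAP 4.1 ties the tests to that table: "Statistical tests will be 2-sided and will be conducted at the significance level provided in" Table 12-1.

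**Stopping.** If the interim p-value is below the boundary, "the study may be stopped for efficacy, or continue as planned as decided by the Sponsor".

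**Interim outputs.** SAP 12 says the DUX4 results "will be presented to the Sponsor as group-level summaries of the unblinded data with associated p-values" and refers to the table list in SAP 15.8. There, Table 14.2.2.1.1 (change from baseline in DUX4 Score 1, FAS) is marked for both topline and IA. Neither SAP 12 nor Protocol 5.6 mentions a confidence interval for the interim.

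**Not found.** The supplied text specifies no repeated or stage-wise interval, no bias-adjusted estimate, and no caution about the estimate after an early stop.

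**The concern.** When the interim look was added, the p-value was given a look-specific level but the interval was not. Two separate consequences follow.

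- **Interim not crossed.** A 95% CI excludes zero whenever p<0.05, while the boundary requires p below 0.000567 to 0.004027. The sponsor, who decides whether to stop, can therefore be looking at an interval that reads as an established effect beside a test that has not been passed.
- **Interim crossed and study stopped.** The interval and test then agree about zero. But only extreme estimates can stop the study, so the plain LS-mean difference overstates the effect and the 95% CI is centred too high. If the study stops, these become the reported result.

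The plan says the interim is meant to inform further development, so the size of the estimate matters as well as its significance.

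**Working it through.** **Inputs.** Effect size 0.70, 68 evaluable subjects, 1:1 allocation (Protocol 7.3); alphas and exit probabilities (Protocol 7.6.8, Table 7-1). The text of 7.6.8 rounds the interim alphas to 0.001 and 0.004; the table values are used here. The model is a two-sample t comparison with SD 1, so SE = √(4/n) and df = n−2. This omits the ANCOVA covariates.

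**1. The plan's own figures.** Spending at information fraction n/68 is 2[1−Φ(1.96/√(n/68))].

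| | 22 pairs: plan | 22 pairs: recomputed | 32 pairs: plan | 32 pairs: recomputed |
|---|---|---|---|---|
| Interim alpha | 0.000567 | 0.000569 | 0.004027 | 0.004275 |
| Final alpha | 0.049755 | 0.049754 | 0.048405 | 0.048275 |
| Interim exit at 0.70 SD | 2.3% | 2.1% | 13.9% | 15.2% |
| Cumulative exit | 82.3% | 82.25% | 82.2% | 82.0% |

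The design at 22 pairs reproduces closely. The match at 32 is approximate, but not far enough off to change the conclusion.

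**2. CI levels that match the tests, 100(1−alpha)%.**
- Interim: 1−0.000567 = 99.94% at 22 pairs; 1−0.004027 = 99.60% at 32.
- Final: 1−0.049755 = 95.02%; 1−0.048405 = 95.16%.

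At 0.70 SD, a final p-value falls between the final alpha and 0.05 in only 0.06% (22) to 0.4% (32) of trials.

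**3. Interim 95% CI excludes zero, boundary not crossed.** This is P(p<0.05) − P(cross), from the noncentral t at 0.70 SD.
- 22 pairs: 0.346 − 0.021 = 0.325.
- 32 pairs: 0.483 − 0.152 = 0.331.

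Under no effect the corresponding figure is 4.6–4.9%.

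**4. Hand check at the boundary** (sample SD equal to the true SD).
- 22 pairs: critical t is 4.092 and SE is √(4/22) = 0.426, so the difference must reach 4.092 × 0.426 = 1.74. The lower 95% limit there is 1.74 − 2.086 × 0.426 = 0.86, already above 0.70.
- 32 pairs: critical t is 3.115 and SE is √(4/32) = 0.354, so the difference must reach 1.10. The lower limit is 1.10 − 2.042 × 0.354 = 0.38, below 0.70.

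**5. Simulation given a stop, true effect 0.70** (3 million trials per case).

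| | 22 pairs | 32 pairs |
|---|---|---|
| Mean estimate (SD units) | 1.58 | 1.21 |
| Ratio to truth | 1.58/0.70 = 2.25 | 1.21/0.70 = 1.73 |
| 95% CI contains 0.70 | 16–17% | 83% |
| Boundary-level CI contains 0.70 | 98.6–98.7% | 98.7% |

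At 22 pairs the mean is below the 1.74 of step 4 because a small sample SD also helps a trial cross. A normal approximation gives 95% CI coverage of 30% (22) and 86.5% (32).

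**6. Dependence on the true effect** (t-based coverage of the 95% CI after a stop at 22 pairs): under 1% at 0.5, 16–17% at 0.70, 53% at 0.9, 67% at 1.0. At 32 pairs it is 58% at 0.5 and 94% at 1.0.

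**7. Over all trials, stopped or continued, at 0.70.** Coverage is 93.7% (22) and 94.4% (32), with a mean reported estimate of 0.71 and 0.74. A stop whose interval misses 0.70 occurs in about 0.021 × 0.837 = 1.8% of trials at 22 pairs and 0.152 × 0.165 = 2.5% at 32.

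**The case against.** Several points against the concern are sound, and they bound it.

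- **Every decision rule reads the p-value.** The stopping rule, the testing hierarchy and the primary test all compare p with the look-specific alpha. A reader might note that under no effect at least one of the two 95% CIs excludes zero in 8.9% (22) or 8.4% (32) of trials, and infer an inflated Type I error. The documents do not support that, because no claim rests on the interval.
- **The final look is not affected in practice.** A reader might infer that the intervals conflict with the tests at both looks. Step 2 shows the final mismatch is negligible, and the sentence quoted from 7.6.2 sits in text about the final p-value.
- **After a stop, interval and test agree about zero.** The disagreement in step 3 arises only when the boundary is not crossed, and it partly reflects the strictness of any O'Brien-Fleming interim boundary.
- **A stop is optional, and unlikely at 22 pairs.** A reader might infer that the trial's 95% CI usually misses the truth. That holds only for a stop near 22 pairs with a true effect around or below the planned one. At 32 pairs, or with a larger effect, coverage is much better, and across all trials it is near nominal.
- **The interim CI is inferred.** SAP 12 and Protocol 5.6 mention summaries and p-values only, and the shells are in a separate document.

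What remains is narrower. Near-nominal average coverage does not help the reader of a trial that has stopped, and the plan says nothing about which interval that reader should be given.

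**Conclusion.** The point stands as a gap in reporting at the interim look and after an early stop. It is not a flaw in error control or in the final analysis. At the planned 0.70 SD, the 95% CI excludes zero without the boundary being crossed in about a third of interim looks. If the study stops, the unadjusted estimate averages about 2.25 times the truth at 22 pairs and 1.73 times at 32. The 95% CI contains the truth in about 16–17% (30% by normal approximation) and 83% of those stops.

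These figures rest on a two-sample t model without covariates, 68 evaluable subjects, a true effect of 0.70 SD, and a stop whenever the boundary is crossed, although the plan leaves that to the sponsor. Coverage after a stop at 22 pairs is sensitive to the true effect. The presence of the CI in the interim output rests on the IA flag together with SAP 8.2. The change is worth making because it is cheap and because an interval chosen after the unblinded interim results are known would carry less weight.

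**What to change.** In Protocol 7.6.2 and 7.6.8 and SAP 8.2 and 12:

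1. Report the interim primary treatment difference with a CI at 100(1−alpha)% from Table 7-1/12-1 for the actual number of pairs (99.94% at 22, 99.60% at 32), or with a prespecified stage-wise interval.
2. State that this is the reported interval if the study stops early, with a sentence that the point estimate overstates the effect after a stop.
3. Optional: set the final CI to the final alpha (95.02–95.16%), and add a bias-adjusted estimate after a stop.

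The cost is a few lines of text and, for the boundary-level interval, one CI-level setting in the existing program. The price is a wider interval at the interim or after an early stop. A boundary-level interval restores coverage and agrees with the test by construction, but it leaves the point estimate unchanged; hence the cautionary sentence.

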1.1 Background

Facioscapulohumeral muscular dystrophy (FSHD) is a rare disabling disease with an estimated worldwide population prevalence of between 1:15,000 and 1:20,000 ([Statland and Tawil, 2014](#)), or approximately 16,000 to 21,000 affected individuals in the United States. A higher prevalence rate of 12/100,000 was reported in a population-based study in the Netherlands ([Deenen et al, 2014](#)). About two-thirds of cases are familial-inherited in an autosomal dominant fashion, and one-third are sporadic. FSHD is characterized by descending progressive skeletal muscle weakness affecting the face, shoulders, arms, and trunk, followed by weakness of the distal lower extremities and pelvic girdle. Symptoms typically first appear later in the second decade of life but can begin at any age ([Tawil et al, 2015](#)). Most cases present with shoulder girdle weakness, which is eventually found in nearly all patients ([Padberg, 1982](#)). Muscle biopsies show myopathic or dystrophic changes, including variability in fiber size, rounded fibers, central nuclei, necrotic or regenerating fibers, increased connective tissue, and fatty deposition. Up to one-third of muscle biopsies show a lymphocyte-predominant perivascular inflammatory infiltrate ([Statland et al, 2015b](#)). Muscle strength, as measured by quantitative muscle testing, decreases at an average rate of 1% to 4% per year ([Statland and Tawil, 2014](#)). The most frequent newly developed functional motor limitations include difficulty getting up from lying down in bed and difficulty using arms for activities of daily living ([Statland and Tawil, 2014](#)). The 6-year risk of wheelchair use is 24% ([Statland et al, 2015a](#)). All quality of life domains on the 36-Item Short Form Health Survey are significantly impaired, and over half of patients with FSHD report at least mild to moderate pain ([Moris et al, 2018; Padua et al, 2009](#)). Asymmetry of muscle involvement is common. Cardiac muscle is spared, and respiratory muscles are involved in a minority of patients.

FSHD is caused by aberrant overexpression of the double homeobox 4 (DUX4) gene, a homeobox transcription factor. DUX4 is located within D4Z4 macrosatellite repeats on chromosome 4q35 and is not normally expressed in adult skeletal muscle when the number of repeats is >10. Approximately 95% of patients with FSHD have type 1 (FSHD1), in which the D4Z4 repeat array is contracted to 1 to 10 units on one allele ([Lemmers et al, 2010; Statland and Tawil, 2014](#)). FSHD patients carrying a smaller number of repeats (1 to 3 units) are, on average, more severely affected ([Tawil et al, 1996](#)). Loss of these repetitive elements (referred to as contraction) leads to de-repression of the D4Z4 locus and expression of DUX4

Fulcrum Therapeutics

Losmapimod

Protocol FIS-002-2019, Version 4.0 (COVID-19 Pandemic Emergency Amendment)

10 April 2020

([de Greef et al, 2008](#); [Statland and Tawil, 2014](#)). Stable inherited transmission of the repeat is reported within affected families and kindreds, with the most comprehensive analysis conducted on a larger Utah kindred in which the repeat size is the same in multiple, distantly related branches ([Flanigan et al, 2001](#); [Lemmers et al, 2004](#)). Patients with FSHD type 2 (FSHD2) have a pathological mutation in a key regulatory protein encoded by the structural maintenance of chromosomes flexible hinge domain 1 (SMCHD1) gene, resulting in reduced methylation of the D4Z4 repeat array and aberrant *DUX4* expression ([Lemmers et al, 2012](#)). *DUX4* pathological activation in skeletal muscle as a result of the D4Z4 repeat contraction (in FSHD1) or SMCHD1 mutations (in FSHD2) leads to a large, well-characterized transcriptional deregulation cascade ([Bosnakovski et al, 2014](#); [Homma et al, 2015](#); [Jagannathan et al, 2016](#); [Shadle et al, 2017](#); [Yao et al, 2014](#)). *DUX4* transcriptional deregulation results in the activation of innumerable pathological cell processes, including inflammatory and immune signaling, oxidative stress, and programmed cell death. The end result of aberrant *DUX4* activity is myofiber death with the replacement of skeletal muscle by fat, resulting in a clinical manifestation of progressive loss of strength and accumulation of physical disability.

Compounds that reduce *DUX4* and its *DUX4*-regulated transcripts should provide a robust disease-modifying therapeutic approach for the treatment of FSHD at its root cause.

There are currently no approved disease-modifying treatments for FSHD. Low-intensity aerobic exercise tailored to the patient's distribution of weakness may provide limited beneficial effect ([Janssen et al, 2016](#)). Limited range of motion in the shoulder girdle stems from periscapular muscle weakness; in such cases, surgical scapular fixation (scapulodesis) can result in some functional improvement for select patients ([Tawil et al, 2015](#)). Very few compounds are currently in clinical development for FSHD, and no therapy has been proven to reduce disease severity or delay the progression of the disease; therefore, there is a high unmet need for an effective therapy for FSHD.

Fulcrum is developing losmapimod, a selective p38 α and β kinase small molecule inhibitor that specifically reduces *DUX4* in FSHD myotubes, for treatment of FSHD. Extensive exposure and safety data from previous clinical studies with losmapimod provide robust evidence supporting its safety and tolerability, including during chronic dosing, and provide a rationale for the dosing regimen selected. This study will evaluate the efficacy and safety of losmapimod in treating subjects with FSHD1.

Fulcrum Therapeutics

Losmapimod

Protocol FIS-002-2019, Version 4.0 (COVID-19 Pandemic Emergency Amendment)

10 April 2020

